4.5 Exclusion Criteria

Women with severe obstetric complications and serious psychiatric disorders will be excluded.

4.6 Selection of the Participants

Potential participants will be identified during routine ante-natal care (ANC) visits at the City of Harare Polyclinics. The potential participants will be briefed about the study and those who verbally agree to participate in the study will be given the participant information sheet to allow voluntary participation and informed decision. All mothers with a positive HIV status will be encouraged to enrol in the study. HIV negative mothers will be recruited systematically.

4.7 Sampling Procedure

The whole population of HIV+ mothers and systematic sampling of HIV- mothers will done. For very HIV positive pregnant mother, the 10th HIV negative mother will be recruited, taking cognisance of the 12% HIV prevalence in this population.

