I agree to conduct this clinical study in accordance with the design and specific provisions of this protocol and will only make changes in the protocol after notifying the sponsor.

I understand that I may terminate or suspend enrolment of the study at any time if it becomes necessary to protect the best interests of the study participants.

I agree to personally conduct and supervise this investigation to ensure that all associates, colleagues, and employees assisting in the running of this study are informed about their obligations in meeting these commitments.

I will conduct the study in accordance with Good Clinical Practice, the Declaration of Helsinki, and the moral, ethical and scientific principles that justify medical research. The study will be conducted in accordance with all relevant laws and regulations relating to clinical studies and the protection of study participants.

I will ensure that the requirements relating to HREC review and approval are met.

I agree to maintain adequate and accurate records and to make those records available for audit and inspection in accordance with relevant regulatory requirements.

I agree to promptly report to the HREC any changes in the research activities and all unanticipated problems involving risks to human subjects or others. Additionally, I will not make any changes in the research without HREC approval, except where necessary to ensure the safety of study participants.

Principal Investigator

Name	Signature	Date
Co-Investigator		
Name	Signature	Date
Co-Investigator		
Name	Signature	Date

Protocol Summary

Full Title	HIV Exposure, Disease Acquisition and Progression Among Children: Role of Maternal Immunogenetics,
	Viral Genetic Diversity, HAART Exposure, Co-morbidities and Psycho-Social Status: UZ-CHS Birth
	Cohort
Short Title	UZ-CHS Birth Cohort
Study	Prospective cohort study
Design	riospective conort study
Study	Pregnant women from 28 weeks gestation and their infants
Population	
Sample size	1200 (600 HIV positive (+) and 600 HIV negative (-)
Duration of	A total of 27 months that is, plus or minus 3 months in pregnancy and a follow up period of 24 months
participation	after delivery.
Study	An observational study on how antenatal co-morbidities impact on pregnancy outcome, infant growth and
intervention	development in this era of option B+ of prevention of mother to child transmission of HIV (PMTCT).

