Background	Whilst the numbers of human immune deficiency virus (HIV) exposed and infected (HEI) infants are dwindling by the day, courtesy of the current effective PMTCT programs, the converse is true with (HIV) exposed but uninfected (HEU) infants. Despite being HIV uninfected HEU infants, have been shown to have higher morbidity and mortality mainly from infectious diseases just like their HEI counterparts. Understanding why and how this ever growing population of HEU infants is at high risk of acquiring infections is critical as their problems will be of major public health importance in the near future. However, before understanding HEU infants themselves, it is necessary to first understand the impact of theintrauterineenvironment which is key in shaping their immune development and their lifelong health in general. To achieve this, a new research paradigm involving an integrated approach is critical. There is need to clearly discern, in a holistic and synergistic approach involving different specialties, the role of antenatal comorbidities including maternal psychosocial well-being not mention the impact of highly active antiretroviral therapy (HAART) prophylaxis regimen on pregnancy outcome, infant growth, immune and/or neuro-development. More so, how similar or different these factors are among HIV+ and HIV- pregnant women remains poorly described. Evaluation of combinations of soluble biomarkers of different comorbidities may prove more powerful tool in predicting disease outcome. Undertaking research in such a manner within the college not only provides the mostly sought after evidence based clinical care for mothers and their children but also build research capacity within the College. In addition investigators also attain higher degrees for self-actualization not to mention institutional and national professional advancements.
Primary	1. To determine the prevalence and incidence of HIV and co-infections (hepatitis B virus (HBV) hepatitis
Objectives	C virus (HCV), cytomegalovirus(CMV)intestinal parasites) and determine how these impact on
	pregnancy outcome, infant growth and immune/neuro-development.
	 To determine of maternal nutritional status and the prevalence and incidence of non-communicable
	diseases (diabetes, hypertensive disorders, cardiovascular diseases) and how these impact on pregnancy
	outcome and child growth
	3. To determine immunological and soluble biomarkers of HIV transmission, diseases progression for

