3.1 Main Objective

This study aims to establish a birth cohort to investigate the role of HIV and comorbidities on vertical HIV transmission, immune development and disease progression in children 0-2 years, HEU, HEI and HUU as the control group.

Objectives

A. All Mothers Regardless of HIV Status

- To determine the prevalence and incidence of coinfections (intestinal parasitic infections, HBV, HCV, CMV) malnutrition and non-communicable diseases (NCDs) (gestational diabetes mellitus, hypertensive disorders and CVD) risk factors over 24 months and relate all these comorbidities to:
 - a. Pregnancy outcome, infant growth, development, morbidity and mortality
 - b. Biomarkers of inflammation and immune activations

Infants

- 2. To determine vertically transmitted infections and incidence non-communicable diseases among infants.
- 3. To determine clinical and immunological profiles of HEI, HEU and HUU infants.

B. HIV+ Mothers: Chronic HIV infections

- 1. To determine vertical transmission rates of mothers with acute and chronic HIV infection on option B+
- 2. Determine any association(s) between different option B+ drug regimens, adverse pregnancy outcome, viral load suppression and CD4/CD8 counts on mothers and their infants

C. HIV+ Mothers; Acute HIV infections,

- 1. To determine the incidence of HIV in the postpartum period over the 2 years
- 2. To determine the viral set points, HIV suppression trends and biomarkers of immune activation
- 3. To determine the HIV and host genetic diversity and possible transmission linkages

Infants

To characterise natural killer cell phenotype and function longitudinally from cord blood at birth up to 2 years and relate to infant HIV acquisition , morbidity and mortality

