4.0 Methodology

4.1 Study Design

A prospective cohort study of 1200 pregnant women (600 HIV positive and 600 HIV negative). **Figure 1** below is the study flow diagram.

Viral load re-testing with be done for all Unsuppressed HIV load every 3 months

Figure 1: Study Flow Diagram

Key

*Pregnancy outcome include spontaneous abortions, birth defects, multiple births, low birth weights preterm infants, birth with prolonged hospitalization, birth requiring neonatal intensive care, maternal, perinatal and infant deaths.

**Coinfections include HBV, HCV, CMV and intestinal parasites

***NCD, non-communicable diseases (hypertensive disorders, malnutrition, diabetes)

**** For acute HIV infections ONLY

*****Adverse feotal outcomes include preterm birth (<37 weeks of gestation) low Apgar score<7, low birth weight, Fetal macrosomia, birth weight of more than 4,000 grams, birth defects, stillbirth (death of a fetus weighing \geq 500g or \geq 22 weeks gestation if weight is unavailable), early neonatal death (death between 0-6 days of life), neonatal death (death within the first 28 days of life), neonatal jaundice, infant death, intensive care unit admission, hospital admissions including documented local clinic treatments

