4.10.18 Sample Size Determination

Pocock's formula was used to determine sample size (n) required:

- $n = \frac{p_1(1-p_1)+p_2(1-p_2)(Z_{\alpha}-Z_{\beta})^2}{(p_1-p_2)^2}$
- Where p_1 and p_2 are proportion of success in population 1 and 2
- Z_{α} and Z_{β} are values of standard normal distribution
- α = Significance level
- $\beta = Power$

3% incidence rate has been assumed to factor in for the a high risk of vertical transmission in the breastfeeding period for the few anticipated acute HIV infection²³⁴.With the advent of cell phones the % loss to follow up may not be that bad and cannot be similar for the first and second year. Factored in the worst case scenario of a 15% and 20% loss to follow-up during the first and second year respectively, a minimum sample size required computed using **STATA** is 1200 (600 HIV+ and 600 HIV-) mothers. Assuming a 15% and 20% loss to follow up in the first and second year of the study respectively, should leave us with at least the 417 infants. The sample size has power to predict diseases outcomes of HEU children which must culminate in their improved management. The sample size has not factored in sample sizes of sub-studies linked to it in the **Appendices' Section 6.2**. Should there be sub-studies, they should fit within this parent protocol. These aim to address all the research gaps highlight throughout the literature review.

	a) HIV Chronic Infection		b) HIV Acute Infection	c) HIV Negative	Outcomes
Comorbidities	Treatment experienced Immune	Treatment naive Profiles for dif	ferent comorbidities c	ombinations	Prevalence and incidence of comorbidities, comorbidities trends relating comorbidities to
HBV HCV CMV					immunological profiles, pregnancy outcomes, vertical transmission of infections, patterns and
Anaemia Diabetes Nutritional Status					transmission linkages, infant/child growth and neurodevelopment
Hypertensive disorders					

Table 5: Pictorial Depiction of the Stratification

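### The sampling interval of 10 in section 4.7 does not follow from the 12% HIV prevalence given for it, and the rule as written does not by itself give 600:600

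*Protocol*

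**What the plan says.** Section 4.7 takes all HIV-positive women and a sample of the others: "The whole population of HIV+ mothers and systematic sampling of HIV- mothers will done". The rule follows: "For very HIV positive pregnant mother, the 10th HIV negative mother will be recruited, taking cognisance of the 12% HIV prevalence in this population". Its opening is read here as meaning each HIV-positive mother. Section 4.6 adds only that "HIV negative mothers will be recruited systematically".

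The intended group sizes are equal and are stated three times: in the Protocol Summary ("1200 (600 HIV positive (+) and 600 HIV negative"), in section 4.1 ("A prospective cohort study of 1200 pregnant women (600 HIV positive and 600 HIV negative") and in section 4.10.18 ("is 1200 (600 HIV+ and 600 HIV-) mothers").

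The protocol does not say where the count to 10 starts, what happens when two HIV-positive women lead to the same HIV-negative woman, or whether a group closes at 600.

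On objectives, the first primary objective in the summary begins "To determine the prevalence and incidence of HIV and co-infections". The corresponding objective in section 3.1 reads "To determine the prevalence and incidence of coinfections (intestinal parasitic infections, HBV, HCV, CMV) malnutrition and non-communicable diseases". For HIV itself, section 3.1 lists vertical transmission and postpartum incidence, not prevalence.

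**The concern.** The 12% prevalence is the only reason given for the interval of 10, and it does not lead to 10. The sentence can also be applied in more than one way in the clinics, and neither direct application produces 600 HIV-negative women by the time the HIV-positive group is full. At stake are the balance of the two groups, the number of women to be screened, and uniform selection of the women whose infants form the HIV-unexposed control group.

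The objective is a smaller, separate matter. Group sizes are fixed by design, so the share of HIV-positive women in the cohort carries no information about HIV prevalence.

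**Working it through.** **Inputs.** Prevalence p = 0.12 and interval k = 10 (section 4.7); target 600 HIV-positive and 600 HIV-negative (summary, 4.1, 4.10.18). Assumption: equal eligibility and consent in both groups, because the protocol gives no rates.

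**1. Can 10 be reproduced from 12%?**
- HIV-negative women per HIV-positive woman: (1 − p)/p = 0.88/0.12 = 7.33.
- All women per HIV-positive woman: 1/p = 8.33.
- Neither is 10. An interval of 10 fits p = 1/11 = 9.1% when HIV-negative women are counted, or 1/10 = 10% when all women are counted.

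**2. Every 10th HIV-negative woman is taken.**
- Women seen by the 600th HIV-positive woman: 600/0.12 = 5000.
- HIV-negative among them: 5000 × 0.88 = 4400.
- Sampled: 4400/10 = 440, which is 160 (27%) below 600.
- The result depends on prevalence: 600(1 − p)/(10p) gives 600 at 9.1%, 540 at 10%, 440 at 12% and 340 at 15%.

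**3. The 10th HIV-negative woman after each HIV-positive woman is taken.**
- If one HIV-positive woman is directly followed by another, both counts end at the same HIV-negative woman. Only the last of a run of HIV-positive women adds a new one, and a given HIV-positive woman is the last of her run with probability 1 − p.
- Expected distinct HIV-negative women: 600 × (1 − 0.12) = 528, which is 72 (12%) below 600.

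Simulation of women registering in random order (300 runs each, counted at the 600th HIV-positive woman) gave means of 440 for step 2 and 527 for step 3. The latter is just under 528 because the last counts are still open.

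**4. With a replacement rule added.** If the next HIV-negative woman is taken whenever the 10th is already enrolled, each HIV-positive woman brings one HIV-negative woman. Simulation at 12% gives about 598 at the 600th HIV-positive woman, and the 600th HIV-negative woman about 12 registrants later. This rule is an addition; the protocol does not contain it.

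**5. Continuing to 600 HIV-negative women under step 2.** This needs 6000 HIV-negative women, so 6000/0.88 = 6818 women seen instead of 5000 (6818/5000 = 1.36). If all HIV-positive women are still taken meanwhile, they number 6818 × 0.12 = 818.

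**6. Cost in precision.** Standard error of a two-group difference relative to 600:600, with equal variances: √[(1/600 + 1/n)/(2/600)].
- n = 440: √1.182 = 1.087, about 9% higher.
- n = 528: √1.068 = 1.034, about 3% higher.

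**7. HIV prevalence from the cohort.** 600/1200 = 50% by design, whatever the prevalence among antenatal women.

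**The case against.** The strongest reply is that section 4.7 speaks of one HIV-negative woman for each HIV-positive woman. That is 1:1 by intention and agrees with the 600:600 stated elsewhere. On that view the interval does not set the ratio, and the mention of 12% is a loose remark rather than a derivation. As a statement of intent this stands. It does not rescue the rule as written: taken literally it gives about 528 distinct women, and reaches 600 only with the unstated replacement step. The 12% remains the only basis given for 10 and does not lead to it.

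A second reply is that the 600 HIV-negative women are a stated target and nothing says their recruitment stops early. This also stands. A reader might infer from step 2 that the control group will end 27% short. The documents do not support that: it requires the every-10th reading and recruitment of HIV-negative women ending when the HIV-positive group fills. Nor is bias shown, since every 10th woman is still a valid systematic sample.

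Third, uptake may differ. If uptake among HIV-positive women were 7.33/10 = 73% of that among HIV-negative women, an interval of 10 would give 1:1. The protocol gives no such figure.

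On the objective, it can fairly be said that only one summary phrase is involved. The primary end points concern comorbidities within HIV-positive and HIV-negative mothers, and section 4.10.24 lists HIV incidence and transmission. A reader might infer that the study means to report 50% as an HIV prevalence; no passage proposes that calculation.

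**Conclusion.** The point holds, as a minor one. An interval of 10 does not follow from 12% prevalence, which implies about 7.3. With equal uptake and registration in random order, the rule as written gives about 440 or about 528 HIV-negative women when the 600th HIV-positive woman is enrolled, depending on how it is applied.

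The consequence is for recruitment balance and screening load, not validity: up to 36% more women screened if every 10th is taken until 600 is reached, or a standard error at most about 9% higher if recruitment stopped at 600 versus 440. It would be equally wrong to conclude that the rule secures 1:1 whatever the prevalence, because that depends on a replacement step the protocol lacks.

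The HIV-prevalence wording in the summary's first primary objective cannot be met from a cohort fixed at 600:600 and differs from section 3.1.

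**What to change.** In section 4.7, state one counting rule that gives 1:1. Either of these would do:
- one HIV-negative woman per HIV-positive woman, namely the 10th after her or the next one when the 10th is already enrolled, with the 12% clause deleted; or
- a systematic interval of about 7, adjusted to the running HIV-positive count. At 12%, a fixed 7 gives about 4400/7 = 629 and a fixed 8 gives 4400/8 = 550, so the adjustment is needed.

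Under either rule, state that each group closes at 600, and limit the sentence on taking all HIV-positive women accordingly.

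In the summary, delete HIV prevalence from primary objective 1 in line with section 3.1, or say that it will be estimated from the antenatal screening counts.

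The cost is a few sentences, plus a screening count if HIV prevalence is kept. No participants are added.

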4.8 Mothers' Procedures

• A questionnaire will be administered at enrolment from which information regarding their sociodemographics, sexual behaviour and reproductive health issues including obstetrical records will be obtained. Antiretroviral use and regimen will be recorded for all the HIV+ mothers. Assessment of nutritional status/BMI will be done using standard anthropometric indices. A physical examination will be done at every visit by the study clinician. Mothers will be enrolled at 28-36 weeks gestation and followed up at delivery, 10 days and 6, 10, 14, 24, 36, 48, 72 and 96 weeks postpartum thus totaling 11 visits during the study period. Data can still be collected in cases of missed visits provided the participant turns up within the seven day window period of the scheduled visits. The participant may be asked to discontinue if she consecutively fails to turn up for at least two successive scheduled study visits without any reason(s).

Biological specimens blood, cord blood, amniotic fluid, breast milk urine and stool will be collected at different visit with the respective quantities and purposes as shown in the **Table** 1 below.

	Total Volume of Specimen Required						
Visit	HIV Status	Blood* (mL)	Stool** (grams)	Breast Milk* (mL)	Urine *** (mL)	Amniotic Fluid (mL)	Cord Blood (mL)
1	HIV+	30	20	-	100	50	
In Pregnancy	HIV-	25	20		100	50	
2 Delivery	HIV+	10	20		100	50	50
	HIV-	5	20		100	50	50
3 7 -10 days pp	HIV+	-	If delivery visit is	10	100		
	HIV-	-	missed some of the samples are collected.	10	100		
4 6 Weeks/1½Months pp	HIV+	20	20	10	100		
	HIV-	10	20	10	100	50	
5 10 Weeks /2½ Months	HIV+	20	20	10	100		
рр	HIV-	10	20	10	100		
6 14 Weeks, 3½Months	HIV+	20	20	10	100		
рр	HIV-	10	20	10	100		
7 24 Weeks/6 Months pp	HIV+	20	20	10	100		
	HIV-	10	20	10	100		
8 36 Weeks/9 Months pp	HIV+	20	20	10	100		
	HIV-	10	20	10	100		
9 48 Weeks/1 year	HIV+	20	20	10	100		
pp	HIV-	10	20	10	100		
10 72 Weeks /1 ^{1/2} years	HIV+	20	20	10	100		
	HIV-	10	20	10	100		
11 96 Weeks/2 years	HIV+	20	20	10	100		
	HIV-	10	20	10	100		

Table 1: Types and total Volumes of Maternal Specimen Required

*Generally blood samples, amniotic fluid cord blood and breast milk will be tested for trend in immune profiles and coinfections.

Stool samples will be tested for intestinal parasites * Urine

urinalysis

Procedure	Specimen	1	2	3	4	5	6	7	8	9	10	11
/Test	Required	Volume/gra	labour	7-10 Day	6 wks	10 wks	14 wks	24 wks	36 wks	48 wks	72 wks	96 wks
	(volume)	m		рр	рр	рр	рр	рр	рр	рр	рр	рр
CMV / HBV/ HCV	serum(1 mL)	✓ (1
HIV testing/all negatives	Plasma (1 mL)	1	~	1	1	1	1	1	~	1	1	1
STI serology												
Parasites At least 3 specimens	Stool(10 g) Anal swab	1	1	1	1	1	1	1	1	1	1	1
FBC/Differentials/pla telets	Plasma (5mL)	√			1		1			1		1
Markers of immune	Blood (10mL)	1		✓	✓	✓	1	1	1	1	1	√
activation, cytokines levels and trends	Cord blood (10mL)		~									
	Amniotic fluid (10mL)		1									
	Breast milk(10 mL)			1	1	1	1	1	1	1	1	1
Urine	urinalysis	1			1			1				1
Biochemistry	Plasma (5 mL)	✓			1		1			1		1
Panel	Sugar (3 mL)	√			✓		1			1		✓
Restriction factors	Cord blood		✓									
	Breast milk			1	✓	✓	✓	1	✓	1	✓	✓
				FOR	HIV POSI	TIVES ONL	Y					
T cell profile	PBMCs	✓						1	✓	 ✓ 	1	 ✓
HIV RNA load*	Whole blood	√ *										
HLA/KIR host genetics												
HIV genetic diversity for Transmission linkages**	Whole blood	~										V

Table 2: Type, Volume, intervals of collection and Purpose of Maternal Specimens Required

*Re-testing with be done for all Unsuppressed HIV load every 3 months ** for all acute HIV infections

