2.1 Main Hypotheses

- There is no difference in the prevalence and incidence of co-morbidities (anaemia, malnutrition, hypertension, diabetes, HCV, HBV, CMV) and immune profile of HIV+ and HIV- pregnant women and the impact of these comorbidities on pregnancy outcome and infant growth and development within 24 months post-delivery is similar.
- 2. There is no difference in biomarkers of inflammation and immune activation profiles among HIV+ and HIV- mothers with different comorbidities and their HEI, HUU HEU infants.

3.0 Project Goals:

- 1. The main goal of this study is to characterise co-morbidities, immunogenetics of pregnant women and their infants in Harare and ascertain their roles in disease acquisition and transmission
- 2. Contribute to the knowledge base on the role of HIV and human immunogenetics on acquisition and disease progression and co-infections in children.

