4.10.15.1 Infant Measurements

Among children 6-60 months old assessment for acute malnutrition will be done using the 2009,

WHO and UNICEF recommendation of a MUAC cut off value of <11.5 cm

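### The last visit is at 96 weeks after delivery (22.1 months), but the protocol states its follow-up and postpartum end points as 24 months or 2 years

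*Protocol*

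**What the plan says.** Section 4.8 (Mothers' Procedures) lists the visits after enrolment: "followed up at delivery, 10 days and 6, 10, 14, 24, 36, 48, 72 and 96 weeks postpartum thus totaling 11 visits". A late visit still counts "provided the participant turns up within the seven day window period of the scheduled visits". Table 1, the maternal specimen table, adds month or year labels to the weeks, including "24 Weeks/6 Months pp" for visit 7 and "96 Weeks/2 years" for visit 11. Tables 2 and 4 also end at 96 weeks but give weeks only, and Table 3 gives visit numbers only. No later visit is scheduled.

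Elsewhere the horizon is 24 months or two years:
- The Protocol Summary promises "a follow up period of 24 months" after delivery.
- The first hypothesis in section 2.1 concerns whether the impact of comorbidities on pregnancy outcome and on "infant growth and development within 24 months post-delivery is similar".
- Section 3.1 seeks postpartum HIV incidence over two years and maternal comorbidity incidence over 24 months.
- Section 4.10.5 places the maternal exit hepatitis and CMV screen at 24 months postpartum.
- Section 4.10.3.5 times parathyroid hormone and vitamin D at 6, 12 and 24 months, among other times.

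Section 4.10.15.1 sets the infant arm-circumference (MUAC) rule by age: "Among children 6-60 months old assessment for acute malnutrition will be done", with a single cut-off of 11.5 cm.

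**The concern.** The protocol runs on two clocks that disagree by 8%. Visits are fixed in weeks, while the follow-up claim, the hypothesis and several end points are in months or years. Prevalence and incidence of comorbidities are among the primary objectives and end points, so the length of time an incidence figure covers is part of its meaning. If the 96-week data were published as two-year data, the stated horizon would be one the design does not reach. The labels also meet a rule that depends on true age. A reader who follows the 6-month label in Table 1 would apply the infant MUAC rule to children who are younger than its lower limit.

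**Working it through.** **Inputs.** Visit weeks, labels and the 7-day window are from section 4.8 and Table 1. The 24-month horizon is from the Protocol Summary and sections 2.1, 3.1 and 4.10.5. The MUAC age range is from section 4.10.15.1. The 3% incidence is from section 4.10.18, which gives no time unit, so both readings are shown. One month = 365.25/12 = 30.4375 days.

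**1. The plan's own figures.** The visit count reproduces: enrolment + delivery + day 10 + 8 later visits = 11. The labels reproduce only as weeks/4:

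| Week | Table 1 label (months) | weeks/4 | weeks × 7/30.4375 |
|---|---|---|---|
| 24 | 6 | 6 | 5.52 |
| 36 | 9 | 9 | 8.28 |
| 48 | 12 | 12 | 11.04 |
| 72 | 18 | 18 | 16.56 |
| 96 | 24 | 24 | 22.08 |

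The labels at weeks 6, 10 and 14 (1½, 2½ and 3½ months) follow the same pattern. In every row calendar time is 8.0% shorter than the label. The 27-month participation in the Protocol Summary fits the same convention. From 28 weeks' gestation, with delivery assumed at 40 weeks, the span is 12 + 96 = 108 weeks; 108/4 = 27, but 108 × 7/30.4375 = 24.8 calendar months.

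**2. Shortfall at the last visit.**
- 96 × 7 = 672 days = 22.08 months = 1.84 years.
- 24 × 30.4375 = 730.5 days = 104.4 weeks.
- Difference: 58.5 days = 8.4 weeks; 58.5/730.5 = 8.0%.
- With the 7-day window: 679/30.4375 = 22.3 months at most.

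**3. Effect on a cumulative incidence from delivery.** With constant hazard λ, cumulative incidence = 1 − exp(−λt).
- If 3% is the annual rate: 1 − exp(−0.03 × 1.84) = 5.37% at 96 weeks, against 1 − exp(−0.06) = 5.82% at 24 months. That is 0.45 percentage points, or 7.8% relative.
- If 3% is cumulative by 24 months: λ = −ln(0.97)/2, which gives 2.76% by 96 weeks.
- For rates from 1% to 10% a year, the relative shortfall runs from 7.9% to 7.3%.

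**4. Effect on a rate.** With actual person-time, 3.00 per 100 person-years stays 3.00. With a nominal two years per woman it becomes 3.00 × 1.84/2 = 2.76.

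**5. Effect on a comparison.** Take groups with 5% and 10% a year. At 96 weeks the cumulative incidences are 8.79% and 16.81%, ratio 1.912. At 24 months they are 9.52% and 18.13%, ratio 1.905. The contrast barely moves.

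**6. Infant age rule.** Six months = 6 × 30.4375 = 182.6 days. The 24-week visit is at day 168, or day 175 at the end of the window (5.75 months). An infant seen on schedule is therefore below the range at that visit. The next visit, week 36, is at 8.28 months and inside it.

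**The case against.** The strongest reply is that this is a loose convention used consistently. Dividing by four gives every label in Table 1, so staff can map a 6-, 12- or 24-month test to the 24-, 48- or 96-week visit. Table 2 does place the exit coinfection screen at visit 11. This largely stands for the running of visits. It does not make 96 weeks two years in a reported result, and the convention is nowhere stated.

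A reader might infer more than the protocol supports:

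- *That the data will be analysed as 24 months.* Sections 4.10.21 and 4.10.22 name tests, regression and unadjusted relative risks. They name no incidence estimator, nominal denominator or 24-month analysis, and a person-time rule is commonly left to a statistical analysis plan.
- *That every rate is biased.* Steps 4 and 5 show otherwise: rates from actual dates are right, and both HIV groups share one schedule.
- *That every child will look small for age.* Nothing says infant indices use labelled age. The infant table is headed in weeks, and the MUAC cut-off is one fixed value across its age range.
- *That infant malnutrition cannot be assessed.* The MUAC rule names no visit, the 6-month label is in the maternal table, and weeks 36, 48, 72 and 96 all fall inside the range.

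The time origin also matters. The maternal comorbidity objective gives no starting point. From enrolment at 28-36 weeks, with delivery assumed at 40 weeks, the last visit is 100 to 108 weeks later, or 23.0 to 24.8 months. The shortfall therefore bears mainly on outcomes counted from delivery.

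**Conclusion.** The discrepancy is real and of low severity. Counted from delivery, the schedule ends at 22.1 months, while the protocol states 24 months or two years in its summary, hypothesis, postpartum HIV objective and exit screen. The cost is limited to absolute figures: about 8% relative if a cumulative incidence at 96 weeks is called a 24-month figure, or if a nominal two years per woman is used as the denominator. That size assumes a constant hazard; the 0.45-point illustration also assumes that the 3% is annual. Comparisons between HIV groups and rates from actual dates are little affected or not at all. Separately, one infant time point, the 24-week visit, lies outside the age range of the MUAC rule. None of this threatens the validity of the study.

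**What to change.** - Restate the postpartum follow-up and end points as 96 weeks (about 22 months) in the Protocol Summary and sections 2.1, 3.1, 4.3, 4.4 and 4.10.5, or reconcile the last visit with 24 months.
- Correct the month and year labels in Table 1. Tables 2 to 4 carry none and need no such change. Bring the month-based laboratory times in section 4.10.3.5 into line with the named visits.
- State that person-time and infant age are computed from actual dates.
- Reconcile the 24-week infant visit with the 6-60-month range in section 4.10.15.1, so that it is clear whether the MUAC rule is meant to apply at that visit.

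If the end points are restated, the cost is an edit to the text and a slightly shorter stated follow-up, with no extra visits. Reconciling in the other direction, by changing the schedule, would have operational costs that the protocol gives no figures to estimate.
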